5.2. Populations

HCPs:

HCPs involved in the treatment and management of patients with diabetes who are aware of the insulin product Humalog U-200 KwikPen will be eligible. The respondent population will include a mix of HCPs who have and have not prescribed Humalog U-200 KwikPen. HCPs who have ever worked for or who have family members who have ever worked for Eli Lilly and Company (Lilly), UBC, or the FDA (Food and Drug Administration) will be excluded. Screening questions will be used to determine respondent eligibility.

Patients

Patients will be identified through a PBM partner, which will provide broad demographic coverage and include patients in 50 states and the District of Columbia. Leveraging this partner, a list of patients who are 18 years or older, have diabetes and have filled/refilled at least one (1) prescription for Humalog U-200 KwikPen in the past 90 days will be eligible to participate. Those who have ever worked for or who have family members who have ever worked for Lilly,

UBC, or the FDA will be excluded. Screening questions will be used to determine respondent eligibility.

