3. MILESTONES

Milestone	Planned date
Start of data collection	Estimated August 2016
End of data collection	Estimated November 2016

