Humalog U-200 KwikPen is a prefilled and multi-dose pen-injector device (pen) that delivers insulin lispro by subcutaneous injection to improve glycemic control in adults and children with diabetes mellitus. Compared to Humalog U-100 KwikPen, it contains the same number of units of insulin lispro in half the volume. Despite warning messages on the pen and in the instructions for use, results from Human Factors studies performed in the United States (US) showed that a small percentage of patients may choose to withdraw insulin from the pen cartridge with a syringe if faced with device malfunction. Anecdotal information also indicates that patients may transfer insulin lispro from the pen cartridge into an insulin pump. Because of these data and to further optimize the benefit-risk balance of the presentation, additional Risk Minimization Measures beyond routine risk minimization measures (are being implemented, including communications to Healthcare Professionals (HCPs) and patients to minimize the risk of hyperglycemia and/or potentially hypoglycemia associated with insulin transfer from the pen cartridge to an alternative administration device without concentration adjustment and dose adjustment when transferring from Humalog U-100 KwikPen to Humalog U-200 KwikPen.

The additional Risk Minimization Measures will include a Direct Healthcare Professional Communication (DHPC) that will be distributed to pharmacists and prescribers (endocrinologists and mealtime insulin prescribing primary care physicians, nurse practitioners, and physician's

assistants). A patient communication document will be distributed in the single pen product sample packages that are routinely provided by HCPs to patients who have been newly prescribed Humalog U-200 KwikPen.

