- Extent of understanding of the key safety messages for Humalog U-200 KwikPen, as communicated through risk minimization measures (Were the key safety messages in the patient communication understood by the patient?)
- Extent of recall/receipt of the patient communication in the patient sample upon first prescription of Humalog U-200 KwikPen (Does the patient recall receiving the patient sample which included the patient communication document?)
- Extent of key safety message consideration by patients during administration of Humalog U-200 KwikPen (Will the patient follow the key safety messages communicated during administration of Humalog U-200 KwikPen?)

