5.3. Study Endpoints

The additional Risk Minimization Measures will be considered effective if the majority of respondents demonstrate they are aware of the key safety messages communicated.

HCPs:

- Demonstrating that they understand the key safety messages communicated in the DHPC.
- Reporting they discuss the safe use of the product as defined in the product label and DHPC to their patients who are receiving their first prescription of Humalog U-200 KwikPen.

Patients:

- Demonstrating that they understand the key safety messages communicated about Humalog U-200 KwikPen.
- Reporting that they follow the key safety messages during administration of Humalog U-200 KwikPen.

All statistical analyses will be descriptive, i.e., no formal hypothesis will be tested.

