5.4. Setting

The assessment surveys will be executed and the analysis will be completed within 18 months from product launch.

HCPs:

Eligible HCPs will receive an invitation letter ([APPENDIX I.2](#)) via email if an email address is available, or a letter via the United States Postal Service (USPS). The invitation letter will include: an overview of the rationale for the survey, information on how to access the survey online and by telephone, and a unique User Identification to ensure that the invitation is used only once. For telephone interviews, a trained interviewer, working from a computer-assisted telephone interviewing (CATI) script, will read questions or statements to the HCP. The letter will also contain a unique code that the respondent must provide when accessing the survey via the Internet or telephone. For telephone interviews, a trained interviewer, working from a computer-CATI script, will read questions or statements to the HCP. The average survey is expected to take approximately 15 minutes to complete.

A random sample of HCPs will be recruited to participate in the survey based on the list of HCPs to whom Lilly has provided a DHPC letter. The recruitment letter will indicate that participants will be compensated \$100 for their time and effort in completing the survey with the exception of HCPs who are licensed and practice in Minnesota, Vermont, Massachusetts or the District of Columbia in accordance with state laws. HCPs from these states can elect to participate however they will not be paid. Respondent-identifying information will be collected for the purposes of providing payment.

The response rate will be monitored throughout the data collection period. Reminder notices will be sent via email and or via the USPS. Additional recruitment methods may be explored during survey execution if necessary to achieve a total of 280 completed surveys.

Patients:

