- Distribution of participants by years with diabetes
- Distribution of participants by length of time treated with any injectable insulin therapy
- Distribution of participants by length of time treated with Humalog U-200 KwikPen
- Distribution of participants by length of time of prior insulin use prior to Humalog U-200 KwikPen

Patient responses to questions pertaining to the survey objectives:

- Awareness of the Important Safety Information for Humalog U-200 KwikPen
- Receipt of or access to Important Safety Information
- Understanding of the key safety messages
- Self-reported practices with respect to the key safety messages

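### The receipt/recall question is about first prescription, but the patient survey samples all current users and states only a pooled receipt rate

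*Protocol*

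**What the plan says.** Section 3.1 describes the patient measure as a single contact: "A patient communication document will be distributed in the single pen product sample packages", and those packs are "routinely provided by HCPs to patients who have been newly prescribed Humalog U-200 KwikPen". Section 4 poses the matching process question: "Extent of recall/receipt of the patient communication in the patient sample upon first prescription of Humalog U-200 KwikPen". In the patient survey (Appendix I.3), questions 16A and 16B ask what happened the first time the pen was prescribed.

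The sample is defined differently. Under section 5.2, adults with diabetes who "have filled/refilled at least one (1) prescription for Humalog U-200 KwikPen in the past 90 days will be eligible to participate". Sections 5.6 and 5.11 also accept fills or refills. Survey question 7 asks only whether the pen was ever prescribed. Question 8 records length of use, and patients who have not yet used the pen, who answer in any band up to more than one year, or who do not know all continue.

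In section 5.9, length of use appears only among the participant characteristics: "Distribution of participants by length of time treated with Humalog U-200 KwikPen". The one subgroup analysis named there is medical specialty, for healthcare professionals. Section 5.6 lists receipt of the safety information among the data used to judge effectiveness. Section 5.11 says that a report of non-receipt counts as less than optimal dissemination, and then concedes that respondents may have forgotten.

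On timing, section 5.4 states: "The assessment surveys will be executed and the analysis will be completed within 18 months from product launch". Section 3 gives the end of data collection as "Estimated November 2016". The protocol gives no launch date and no date on which the letter first went into sample packs.

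**The concern.** The 90-day window makes the last fill recent. It does not make the first prescription recent, and the first prescription is what the receipt question is about. A patient who refilled last month may have started more than a year ago.

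A negative answer to question 16A can then mean that the letter was not handed over, that it was handed over and forgotten, or that it was not yet in the packs when the patient started. Only the first is a dissemination failure, yet section 5.11 assigns all reported non-receipt to that reading. The sponsor would respond differently to each, and a single pooled rate cannot tell them apart.

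**Working it through.** **1. The plan's own figure.** Equation 1 in section 5.7 gives half-width = 1.96 × √[p(1−p)/n]. With n = 280 and p = 50, 60, 70, 80, 90%, this is 5.86, 5.74, 5.37, 4.69 and 3.51 points. Table 1 shows 5.9, 5.7, 5.4, 4.7 and 3.5, so it reproduces. These figures apply to a rate over all 280 respondents.

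**2. How old the recalled event can be.** Collection is planned for August to November 2016. November 2016 minus 18 months puts launch no earlier than about May 2015. The 18 months must also cover the analysis, so recall at interview is somewhat under 18 months. Start dates implied by question 8:

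| Length of use | Answered August 2016 | Answered November 2016 |
|---|---|---|
| Less than 3 months | after May 2016 | after August 2016 |
| 3–6 months | February–May 2016 | May–August 2016 |
| 7–12 months | August 2015–January 2016 | November 2015–April 2016 |
| More than 1 year | before August 2015 | before November 2015 |

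Everyone in the last two bands started before the protocol date of 20 May 2016. That does not show that they started before the letter, because the letter's date is not given.

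**3. Size of the mixing (assumed inputs).** Let s be the share of respondents the letter could not have reached, r the receipt rate among the others, and q the receipt reported by the unreachable group. Then pooled rate = (1−s)r + sq, and the shortfall against r is s(r−q). With q = 0:

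| r | s = 0 | s = 10% | s = 25% | s = 40% |
|---|---|---|---|---|
| 60% | 60.0% | 54.0% | 45.0% | 36.0% |
| 70% | 70.0% | 63.0% | 52.5% | 42.0% |
| 80% | 80.0% | 72.0% | 60.0% | 48.0% |

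Allowing some mistaken positive answers changes little: with r = 60%, q = 5% and s = 20%, the pooled rate is 0.8 × 60 + 0.2 × 5 = 49%. The documents give none of s, r and q, and s = 0 is possible. The same formula covers fading recall if s is the share of long-term users and q their remembered receipt, anywhere between 0 and r.

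**4. Precision if receipt is estimated in a subset.** At a 50% rate, if the letter could have reached 75, 50 or 25% of the 280 (assumed), n is 210, 140 or 70 and the half-width is 6.8, 8.3 or 11.7 points. Keeping 280 such patients would need 280/0.75 = 374, 280/0.50 = 560 or 280/0.25 = 1,120 completed surveys.

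**The case against.** Sampling current users suits most of the study. Understanding of the key messages, and whether patients bear them in mind when injecting, are questions about people now using the pen, long-term users included. The pooled understanding rate is a valid description of that group. Only its attribution to the letter is uncertain, and section 5.11 already grants that patients may understand the risks without having received it. This stands, and the point is confined to receipt and recall.

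A reader might infer from the future tense in section 3.1 that longer-term users started before the letter existed. The documents do not support that. The letter may have been in the packs from launch, and elsewhere the protocol writes of the companion letter to healthcare professionals as already sent, so its tenses are a poor guide to timing.

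A reader might also infer that a receipt rate falling below 50% would reverse the study's conclusion. Section 5.3 says: "The additional Risk Minimization Measures will be considered effective if the majority of respondents demonstrate they are aware of the key safety messages communicated". That criterion concerns awareness of the messages. Receipt is a process question with no threshold, so no decision rule is triggered.

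Finally, tables by length of use could sit in the analysis plan, which section 5.10 mentions and which is not shown. That is fair for the tables alone. But the mismatch between eligibility and the first-prescription question, and the reading of non-receipt in 5.11, are protocol text. The general caveat there about forgetting mentions neither time since first prescription nor a start before the letter.

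**Conclusion.** The point holds for the receipt/recall rate. It is asked about first prescription, collected from users of any duration, stated only as a pooled figure, and read in 5.11 as a measure of dissemination. That patients more than a year from first prescription can enter the rate follows from the survey's own answer options. That some could not have received the letter is conditional on its having entered the packs after launch. The combined size cannot be determined from the documents: the table in the working shows what assumed shares would do, and that component is zero if the letter was present from launch. Recall of 18 months is a ceiling that is not reached. This is a cheap improvement to the analysis and interpretation and does not invalidate the survey.

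**What to change.** - **Section 3.1 or 5.4:** state when the letter first went into sample packs, relative to product launch.
- **Section 5.9:** report questions 16A and 16B by question 8 category, showing patients who have not yet used the pen and those who do not know as separate groups.
- **Section 5.9:** answer the receipt/recall question from the length-of-use bands that, at the respondent's survey date, fall wholly after that first distribution date. A fixed cut-off at 6 months would not do: 3–6 months answered in August 2016 means a start in about February to May 2016, which may itself precede the letter. If the letter was present from launch, every band qualifies and the breakdown shows how reported receipt varies with time since starting.
- **Section 5.7:** restate the precision for the subset used.
- **Section 5.11:** say that non-receipt reported by longer-term users may reflect time since first prescription or a start before the letter, and is not by itself evidence of failed dissemination.

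Eligibility and the questionnaire need not change, since length of use is already collected. The cost is a few table columns and a less precise receipt estimate when some bands are excluded.

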5.3. Study Endpoints

The additional Risk Minimization Measures will be considered effective if the majority of respondents demonstrate they are aware of the key safety messages communicated.

HCPs:

- Demonstrating that they understand the key safety messages communicated in the DHPC.
- Reporting they discuss the safe use of the product as defined in the product label and DHPC to their patients who are receiving their first prescription of Humalog U-200 KwikPen.

Patients:

- Demonstrating that they understand the key safety messages communicated about Humalog U-200 KwikPen.
- Reporting that they follow the key safety messages during administration of Humalog U-200 KwikPen.

All statistical analyses will be descriptive, i.e., no formal hypothesis will be tested.

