5.7. Study size

The target sample sizes for the HCP and patient populations are 280 completed surveys for each population. The size of the sample was determined based on both practical and statistical considerations. There is no target comprehension rate specified *a priori*. A sample of 280 completed surveys for both HCPs and patients will allow estimation of the comprehension rate for each key safety message with a moderately high degree of precision. The table below shows the precision of the estimates for level of understanding using two-sided 95% CIs obtained with the sample size of 280 completed surveys. The noted CIs are used to indicate that for any survey-estimated rate of understanding, the true population rate of understanding is at least as high as the lower limit of the 95% CI and may be as high as the upper limit of the 95% CI.

Equation 1

$$95\%CI = Response\ Rate \pm 1.96 \left\{ \sqrt{\left[\frac{Response\ Rate(1-Response\ Rate)}{Sample\ Size} \right]} \right\}$$

Table 1 Sample size calculations

Sample Size	Observed Response Rate* (e.g. Knowledge)	2-Sided 95% CI		
		Half-width	Lower Limit	Upper Limit
280	50%	5.9%	44.1%	55.9%
	60%	5.7%	54.3%	65.7%
	70%	5.4%	64.6%	75.4%
	80%	4.7%	75.3%	84.7%
	90%	3.5%	86.5%	93.5%

*Percentage of responders who correctly answered a question.

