[BEGIN PREAMBLE 2 – DISPLAY ON SAME PAGE AS NEXT QUESTION]

The following questions are about Humalog® U-200 KwikPen®.

[END PREAMBLE 2]

15. Please answer True, False, or I don't know for each of the following statements regarding Humalog® U-200 KwikPen®.

	[RANDOMIZE LIST]	True	False	I don't know
A	Humalog® U-200 KwikPen® is approved for transfer to syringe or pump.			
B	The dose of insulin does not need to be converted when changing patients from one Humalog strength to the other (for example, changing a patient from Humalog U-100 units/mL to Humalog® U-200 KwikPen®).			
C	When prescribing Humalog® U-200 KwikPen®, it is important to clearly indicate the correct strength on the prescription.			
D	It is important to instruct your patients that they should always have a backup pen available.			

16. Are you aware of the Direct Healthcare Professional Communication provided to you by Eli Lilly and Company on the correct use of Humalog® U-200 KwikPen® (*insulin lispro*) to minimize medication errors?

- Yes
- No **[GO TO Q18]**
- I don't know **[GO TO Q18]**

17. Did you read the Direct Healthcare Professional Communication provided to you by Eli Lilly and Company on the correct use of Humalog® U-200 KwikPen® (*insulin lispro*) to minimize medication errors?
- Yes
 - No
 - I don't know
18. Are you aware of the patient communication Patient Information Letter/*IMPORTANT SAFETY INFORMATION FOR* Humalog® U-200 KwikPen® (*insulin lispro*) that is included in patient sample packs of Humalog® KwikPen® provided by Eli Lilly and Company?
- Yes
 - No **[GO TO Q20]**
 - I don't know **[GO TO Q20]**
19. Have you read the patient communication: Patient Information Letter/*IMPORTANT SAFETY INFORMATION FOR* Humalog® U-200 KwikPen® (*insulin lispro*) provided by Eli Lilly and Company?
- Yes
 - No
 - I don't know

[DO NOT DISPLAY QUESTION 20 IF 0 IS SELECTED IN QUESTION 11]

20. Do you or another healthcare professional at your practice discuss the safe use of the Humalog® U-200 KwikPen® to patients receiving their initial prescription?
- Yes
 - No
 - I don't know

[DO NOT DISPLAY QUESTION 21 IF 0 IS SELECTED IN QUESTION 11]

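### Section 5.3 calls the measures effective on an undefined majority while section 5.7 says no target rate exists; read as more than 50% correct, the bar sits at the chance level of a two-way choice

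*Protocol*

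**What the plan says.** Section 5.3 (Study Endpoints) sets a criterion for the study's verdict: "The additional Risk Minimization Measures will be considered effective if the majority of respondents demonstrate they are aware of the key safety messages communicated". It then lists understanding and self-reported behaviour for healthcare professionals (HCPs) and for patients, and closes with "All statistical analyses will be descriptive, i.e., no formal hypothesis will be tested".

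Section 5.7 (Study size) says "There is no target comprehension rate specified" a priori. It justifies 280 completed surveys per population because that number will "allow estimation of the comprehension rate for each key safety message with a moderately high degree of precision". It interprets the interval as meaning that "the true population rate of understanding is at least as high as the lower limit of the 95% CI".

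Section 5.6 says that understanding and behaviour, analysed with descriptive statistics and confidence intervals, will serve to determine effectiveness.

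The knowledge items offer three answers. HCP question 15 has four statements introduced by "Please answer True, False, or I don't know for each of the following statements regarding Humalog® U-200 KwikPen". Patient question 15 (two statements) has the same format, and patient question 16 D and E offer Yes, No or I don't know. Section 5.9 scores *I don't know* as incorrect unless otherwise specified.

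**The concern.** A majority is a target rate of more than 50%, so 5.3 sets what 5.7 says does not exist. Calling the analyses descriptive does not remove the conflict, because 5.3 still issues a verdict of effective or not.

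The rule also cannot be applied as written. It gives no unit (each message, all messages jointly, or a composite) and no deciding statistic (point estimate or confidence limit). Section 5.7 estimates each message separately, whereas 5.3 speaks of the messages collectively.

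Finally, a bar of just over 50% coincides with what random choice between two substantive answers yields. A message that only a minority understands could then be counted as understood. At stake is the effectiveness verdict on communications meant to prevent insulin medication errors.

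**Working it through.** **Inputs from the protocol.** n = 280 per population (5.7); the interval of Equation 1, p ± 1.96·√(p(1−p)/n); three answer options per item (Appendices I.1 and I.3); *I don't know* scored incorrect (5.9).

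**Assumptions, not in the protocol.** Majority means more than 50%, so at least 141 of 280. The share choosing *I don't know* and the share who truly know are unknown and are varied below.

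**1. Table 1 reproduces.** At 50, 60, 70, 80 and 90% observed, Equation 1 gives half-widths of 5.86, 5.74, 5.37, 4.69 and 3.51%, matching the printed 5.9, 5.7, 5.4, 4.7 and 3.5%.

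**2. The smallest passing result on the point estimate.** 141/280 = 50.4%. Half-width = 1.96·√(0.5036·0.4964/280) = 5.9%, so the CI is 44.5 to 56.2%. The measure would pass with an interval that extends well below one half.

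**3. Pure guessing, one item.** If a share d answers *I don't know* and the rest choose at random between the other two options, P(correct) = 0.5(1−d). The exact binomial P(X ≥ 141) is:

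| Answering pattern | P(correct) | P(pass) |
|---|---|---|
| d = 0 | 0.500 | 0.476 |
| d = 5% | 0.475 | 0.185 |
| d = 10% | 0.450 | 0.041 |
| d = 20% | 0.400 | 0.0003 |
| three options equally likely | 0.333 | about 3e-9 |

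**4. Four items, d = 0, independent.** This matches the HCP survey, which has four statements.
- All four must pass: 0.476⁴ = 0.05.
- Any one suffices: 1 − (1 − 0.476)⁴ = 0.92.

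The wording of 5.3 does not say which applies.

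**5. Partial knowledge, one item.** If a share k knows and the others answer correctly with probability g, P(correct) = k + (1−k)g.
- k = 10%, and 10% of the rest say *I don't know*: 0.10 + 0.90·0.45 = 0.505, P(pass) = 0.54.
- k = 20%, and 20% of the rest say so: 0.20 + 0.80·0.40 = 0.520, P(pass) = 0.73.
- k = 30%, the rest split equally over three options: 0.30 + 0.70/3 = 0.533, P(pass) = 0.85.
- Against these, k = 10% with 20% of the rest saying *I don't know*: 0.10 + 0.90·0.40 = 0.460, P(pass) = 0.08.

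**6. A rule on the lower 95% limit.** With 156/280 the lower limit is 49.9%; with 157/280 (56.1%) it is 50.3%. So 157 is the smallest count that passes. Then P(X ≥ 157) is 0.024 at p = 0.5 and 0.92 at a true 60%. The three scenarios in step 5 that passed with 0.54, 0.73 and 0.85 now pass with 0.04, 0.10 and 0.20. If all four messages had to pass at a true 60% each, the probability under independence is 0.919⁴ = 0.71.

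**The case against.** The strongest objection concerns guessing. A reader might infer that guessing alone meets the rule about half the time. The protocol does not support that as a general statement: every item offers *I don't know*, it counts as incorrect, and modest use of it takes the probability from 0.476 to 0.041 or lower. The 0.476 is the top of the range for one item. A reader might likewise quote 0.92, but that requires one passing message out of four to be enough, and nothing in 5.3 suggests this; its wording is plural. Uniform agreement would score three of the four HCP items, but under an all-messages reading it fails on the reverse-keyed transfer item. These limits stand.

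A second objection is that the protocol never says the point estimate decides; 5.6 mentions confidence intervals. That also stands: 141/280 is one reading, and the finding is that the text does not choose. Nor does the protocol show that an analyst would be free to choose after seeing the data, since section 5.10 refers to a survey analysis plan, which may settle the aggregation. HCPs and patients are already listed and reported separately.

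Third, the study yields more than this verdict. Awareness, receipt of the letter and self-reported practice are also reported with intervals, and the guessing argument does not apply to self-reported behaviour.

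None of this removes the conflict between 5.3 and 5.7, which lies within the protocol itself, or the weakness of a bar just above 50% when knowledge is partial.

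**Conclusion.** The point holds as a should-fix. Sections 5.3 and 5.7 contradict each other on whether a target exists, and the 5.3 criterion lacks a unit and a deciding statistic. Read as a point estimate above 50%, it can be met when only a minority knows the answer: probability 0.54 to 0.85 in the three passing scenarios of step 5, but 0.08 in the fourth. Those figures rest on assumed knowledge and answering patterns, on independent respondents, and on the point-estimate reading. The pure-guessing probability for one item runs from about zero to 0.476 and should be quoted only with that range.

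The interval sentence in 5.7 is separately wrong: it presents 95% confidence as certainty that the true rate is no lower than the lower limit.

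**What to change.** Choose one of two routes in 5.3.

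- **Keep a verdict.** State the rule for each key safety message and separately for HCPs and patients: a message counts as understood only if the lower limit of the two-sided 95% CI for the percentage correct exceeds 50% (at least 157 of 280). Name the survey item or items that score each message, and report the percentage of respondents correct on all messages.
- **Drop the verdict.** Delete the effectiveness criterion and report estimates with intervals. This fits the descriptive intent stated in 5.1 and 5.3.

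In 5.7, bring the sentence denying a target rate into line with the choice, and reword the interval sentence as 95% confidence.

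Neither route changes the sample size. The first makes the bar somewhat harder: a message with a true 60% passes with probability 0.92, against more than 0.99 under the 141/280 reading (0.9996 by the same binomial). It also acts much like a formal test, so the statement that no hypothesis is tested should be reconsidered alongside it. Requiring every message to pass, or setting a threshold above 50%, is a further choice for the sponsor and more than a wording change: with four messages at a true 60% each, all pass with probability about 0.71 under independence.
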